The implanted INS will be activated within 14 days after surgical procedure and SCS therapy will be evaluated for the next 12 months. Activation of the device marks the initial time point for effectiveness evaluation of the study therapy after implantation. Assessments of pain intensity, use of medication and study-related adverse events will be made through the 12 month following Device Activation. Additionally, a 3, 6 and 12months after Device Activation, subjects will also be assessed for extent of disability, Patient Global Impression of Change, subject satisfaction and paresthesia. All current subjects or those who have completed their 6-month visit will be offered to return for an additional 12-month visit. This would increase their commitment to the study to 14 months. Figure 1 summarizes the sequence of study-related assessments, procedures, and activities.

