#### **B.6.5. SCS TRIAL PHASE**

Subjects will undergo a Trial Phase with DTM SCS programming. The Trial Phase will last up to 10 days. Percutaneous leads will be placed in the epidural space at a vertebral level based on the subject's pain condition and pain pattern as described in the Physician Implant Manuals. Stimulation will be delivered from an external neurostimulator (ENS).

Anterior-posterior (AP) and lateral X-ray imaging will be done following lead placement at the beginning of the Trial Phase. The subject should flex forward prior to the final AP and lateral X-ray imaging. Additional Imaging may be required if lead migration is suspected throughout the trial.

Stimulation therapy will be as follows:

- Subjects will be given multiple program groups to try. Each DTM SCS program group will have multiple parameters. The stimulation parameters will be within the specifications described in the Intellis™ manuals. Each DTM SCS program group has at least two programs with different pulse rate in the 50 to 1,000 Hz range and each having a maximum pulse width of 1 ms. The subject will progress through each of the program groups until satisfactory pain relief has been reached. The subject will be able to adjust the intensity of the stimulation as deemed needed to obtain pain relief. If sufficient pain relief is not achieved with the initial program group, the subject will be instructed to trial another DTM SCS program group.

Following the standard of care of SCS, adjustments to a program group may be made based on patient feedback following the trialing of a particular program group or set of stimulation parameters. The primary factor for assessing response to a given program group or stimulation parameters is the subject's self-reported pain relief. Adjustments to therapy will be attempted until at least 40% self-reported pain reduction from baseline is achieved or until conclusion of the trial phase (no more than 10 days). Subjects will be assessed for study-related adverse events and medication usage during the duration of the Trial Phase.

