## **B.7. STUDY ENDPOINTS**

### **B.7.1. DEFINITION OF ANALYSIS POPULATIONS**

All subjects who receive a permanent SCS system implant and complete the study without any major protocol deviations (that would render their data unevaluable).

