### **B.7.4. SECONDARY ENDPOINTS**

The following secondary endpoints will be evaluated:

- Change from Baseline in upper limb pain mean VAS score determined at the 3-month visit after device activation. This is calculated as: Change from Baseline in Upper Extremities Pain VAS = 3-Month Visit Pain VAS – Baseline Pain VAS. A negative result reflects a decrease in Pain VAS score, while a positive result reflects an increase in Pain VAS score.
- Change from Baseline in extend of disability as measured by mean Pain Disability Index (PDI), evaluated at 3 months after device activation.
- Frequency of treatment emergent adverse events.

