### **B.8.3. SAFETY**

Safety will be assessed by characterizing study-related adverse events at all study visits with descriptive statistics.

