#### **B.8.3.1 DEFINITIONS**

An adverse event (AE) is any untoward medical occurrence in a subject associated with the use of the therapy under the study whether or not related to the Intellis™ SCS system or the study procedures. An AE is also any event related to any underlying medical condition, present at baseline, which increases in severity or frequency by a clinically meaningful amount during the study as determined by the Investigator. Study-related is defined as relating to device, procedure or therapy.

For all study-related adverse events, the Investigator will provide an assessment of the adverse event, its seriousness, treatment/intervention provided, relationship to the device/procedure/therapy, and resolution.

As the effectiveness measure in this study is upper limb pain, upper limb pain do *not* need to be reported as an adverse event unless it meets the definition of a serious adverse event. Investigators may, however, report any other study pain-related adverse events during the study.

A **serious adverse event** (SAE) is an adverse event that

- Leads to death
- Leads to serious deterioration in the health of the subject, that either results in
  - a life-threatening illness or injury (life-threatening is defined as at risk of death at the time of the event), or
  - a permanent impairment of a body structure or a body function, or
  - in-patient hospitalization or prolongation of existing hospitalization (in-patient hospitalization is defined as a hospital admission for a period of greater than 24 hours), or
  - medical or surgical intervention to prevent life-threatening illness or injury or permanent impairment to a body structure or a body function,
- Leads to fetal distress, fetal death, or a congenital abnormality or birth defect

An **unanticipated adverse device event** (UADE) is a serious adverse event that was not previously identified in nature, severity, or degree of incidence in the Clinical Study Plan, or any unanticipated serious problem associated with a device that related to the rights, safety, or welfare of subjects.

Known adverse events related to the device, procedure or therapy are listed in the section C. (Risk Analysis) of this Clinical Study Plan.

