### **B.8.3.2 REPORTING**

Reported AEs, SAEs and UADEs will be assessed and captured from enrollment through the completion of the study on the Adverse Event Source Worksheet. Study-related is defined as relating to the device, procedure or therapy. The assessment/evaluation can be performed initially by a designee, but the Investigator will make the final determination.

Only adverse events that are evaluated by the Investigator to be study-related will be captured on the CRF.

All study-related adverse events will document seriousness, severity, treatment/intervention provided, relationship to the device/procedure/therapy, and resolution.

AEs and SAEs will be reported as required by the IRB.

As would be the common practice when using commercial medical devices, device - related AEs may be reported by the site (per their institutional policy) to the Customer Service or Technical Support of Medtronic as specified in the manufacturer's labeling/manuals.

Data Monitoring Committee will not be used as this is a post-market open label study and will adhere to all IRB reporting requirements and the device manufacturer's reporting requirements.

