## **B.9. DATA COLLECTION AND ANALYSIS**

### **B.9.1. DATA COLLECTION**

Study data will be collected using paper CRFs. Each data field is expected to have a verifiable source document. Subject confidentiality will be maintained, and each subject will be identified by the assigned study subject number. Subject names will not be published.

Data collection is summarized in Table 1.

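### The secondary safety endpoint is named for treatment emergent adverse events, but the CRF and the safety summary hold only study-related ones, and no adverse event denominator is stated

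*Combined protocol and SAP*

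**What the plan says.** Five parts of the combined protocol and SAP bear on this.

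- **Endpoint.** B.7.4 lists three secondary endpoints. The safety one is "Frequency of treatment emergent adverse events". The term treatment emergent is not defined and is used nowhere else.
- **Summary.** B.8.3: "Safety will be assessed by characterizing study-related adverse events at all study visits with descriptive statistics".
- **Capture.** B.8.3.2 first sends all reported AEs, SAEs and UADEs, from enrollment to study completion, to an Adverse Event Source Worksheet. It then adds: "Only adverse events that are evaluated by the Investigator to be study-related will be captured on the CRF". B.9.1 names the data source: "Study data will be collected using paper CRFs".
- **Definition.** The first sentence of B.8.3.1 ties an AE to use of the study therapy, whether or not the system or procedures caused it. The second widens this: "An AE is also any event related to any underlying medical condition, present at baseline, which increases in severity or frequency". The Investigator must judge that worsening to be clinically meaningful. Study-related means related to device, procedure or therapy.
- **Population.** B.7.1 gives one population: "All subjects who receive a permanent SCS system implant and complete the study without any major protocol deviations". It is assigned to no endpoint. B.9.2 gives no denominator or unit of count for adverse events.

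**The concern.** A reader of the results would take a frequency of treatment emergent adverse events to cover events of any cause with onset under treatment. The planned data can supply only events that the Investigator has judged related. For any given onset window, that filter leaves the count equal or lower, never higher. Collecting safety data is a stated secondary objective (B.2), so the label on this endpoint shapes what can be concluded about it.

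The missing denominator is a second, separate gap. Two analysts could divide by all trialed, all implanted, or the B.7.1 subjects, and each could claim to follow the plan. Nor does the plan say whether frequency counts subjects or events.

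**Working it through.** The documents give no adverse event rate, precision target or safety sample size, so there is no plan figure to reproduce. The check is a comparison of passages, followed by short arithmetic on planned numbers.

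**1. Can the named endpoint be built from the planned data?**

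| Step | Section | Scope |
|---|---|---|
| Endpoint name | B.7.4 | treatment emergent, no causality limit |
| Source worksheet | B.8.3.2 | all reported events |
| CRF | B.8.3.2, B.9.1 | study-related only |
| Safety summary | B.8.3 | study-related only |

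Unrelated events stop at the worksheet. B.8.3.2 also requires seriousness, severity, treatment, relationship and resolution only for study-related events, so worksheet entries for the others may lack those details.

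**2. Is the gap empty under the plan's own definitions?** No, but it may be narrow. The first sentence of B.8.3.1 already links an AE to the therapy, and study-related includes a relation to therapy, so those two sets overlap heavily. The second sentence requires no such link. A baseline condition that worsens materially and is judged unrelated is an AE under B.8.3.1 and is kept off the CRF by B.8.3.2. The number of such events cannot be derived.

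**3. Does the visit text settle the scope?** It is mixed.

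- Study-related: B.6.1 ("Assessments of pain intensity, use of medication and study-related adverse events will be made through the 12 month following Device Activation"), B.6.4, B.6.5 ("Subjects will be assessed for study-related adverse events and medication usage during the duration of the Trial Phase"), B.6.6 to B.6.9, B.6.11 and B.6.12.
- No such limit on the events assessed: B.6.13 (6 months), B.6.14 (12 months) and the remote-visit text in B.6.15.

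The start of capture also differs: enrollment in B.8.3.2, but Baseline as the first mark in the adverse event row of Table 1.

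**4. What would B.7.1 leave out if it were used for safety?** Inputs, all approximate: 55 trialed (B.5.4.1); 45 implanted (Synopsis and B.5.4.1) or 45 completing 3 months (A.3).

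- *If 45 are implanted:* trial-only = 55 − 45 = 10, and 10/55 = 18.2%. Implanted non-completers and major deviations come on top.
- *If 45 complete 3 months, with d implanted subjects lost before then:* implanted = 45 + d; trial-only = 55 − (45 + d) = 10 − d; outside B.7.1 = (10 − d) + d = 10, plus later non-completers and major deviations.

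Either way about 10 of 55 or more fall outside; only the mix differs.

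**5. Does the choice move the reported frequency in a known direction?** No. One subject weighs 1/45 = 2.2 points or 1/55 = 1.8 points. With the same numerator, the two rates differ by a factor of 55/45 = 1.22. The numerator changes too. Assume, for illustration, 5 of 45 with an event (11.1%). If none of the 10 added subjects has an event, the rate is 5/55 = 9.1%; if one has, 6/55 = 10.9%; if two have, 7/55 = 12.7%.

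**The case against.** The strongest reply is that the working rule is clear and only one bullet is out of step. B.8.3 and B.8.3.2 agree with each other, most visit sections and E.3 speak of study-related events, and an analyst who follows them knows what to summarise. Restricting capture to related events may also be deliberate in a post-market study of a commercial device used within its approved parameters. This stands: the capture rule is not the fault, and correcting the label is enough. It does not remove the mismatch, because the bullet that is out of step is the endpoint itself.

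It can also be said that unrelated events are recorded, since the worksheet takes all reported events. That is correct, and a reader who inferred that the plan discards them altogether would go too far. The worksheet, however, is neither the planned data source nor the basis of the planned summary.

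On the denominator, a reader might infer that the plan makes B.7.1 the safety population. The documents do not say so. B.6.6 follows failed-trial subjects for two weeks after lead removal, and B.6.17 follows subjects who withdraw for a study-related event. Neither sits easily with a safety analysis limited to completers. What stands is that no denominator is stated and B.7.1 is the only population on offer.

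**Conclusion.** The point holds in a limited form. Followed as written, the plan reports investigator-assessed study-related events under a broader, undefined name, and it states no denominator, unit of count or consistent onset window for them. The mismatch between name and data, and the absence of a denominator, are plain from the text. That B.7.1 would be used for safety by default is only a possibility.

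Two stronger readings are tempting and unsupported. One is that a large share of events is lost: the first part of the AE definition may make the gap small, and no figure in the documents sizes it. The other is that 18.2% measures an error in safety reporting: it is planned-enrolment arithmetic on two approximate numbers, and the net effect on a reported rate could go either way.

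Severity is minor to moderate. B.9.2 states no hypothesis, all analyses are descriptive, and the primary responder endpoint is untouched.

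**What to change.** 1. In B.7.4, name the endpoint as the frequency of investigator-assessed study-related adverse events. State the onset window, for example from trial lead placement to study exit. Align B.6.13, B.6.14 and the remote-visit text in B.6.15 with B.8.3 and B.8.3.2.
2. In B.7.1, add a safety population of all subjects who undergo trial lead placement, whether or not they are implanted, complete the study or have deviations. Report both the number of subjects with an event over that population and the number of events.

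Both changes are wording only and need no new data collection. The price is a narrower label and possibly less favourable rates, because trial-only subjects and early withdrawals bring in their events.

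If the sponsor prefers to keep treatment emergent, it must define the term and change B.8.3, the CRF rule in B.8.3.2 and the visit sections now limited to study-related events (B.6.1, B.6.4 to B.6.9, B.6.11, B.6.12). That costs more than copying worksheet entries to the CRF: most visits do not now seek unrelated events, and their seriousness and severity are not required.

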## **B.9. DATA COLLECTION AND ANALYSIS**

### **B.9.1. DATA COLLECTION**

Study data will be collected using paper CRFs. Each data field is expected to have a verifiable source document. Subject confidentiality will be maintained, and each subject will be identified by the assigned study subject number. Subject names will not be published.

Data collection is summarized in Table 1.

### **B.9.2. STATISTICAL ANALYSIS**

There are no formal hypotheses evaluated in this study. All baseline and outcome data will be reported using summary statistical methods. Descriptive statistics will be used to summarize baseline and outcome data collected during the study. Continuous variables will be summarized using means, standard deviations, and ranges. Categorical variables will be summarized in frequency distributions.

**Table 1. Schedule of Study Activities**

Activity	Pre-Trial Phase		Trial Phase		Permanent Phase					12 months visit (±31 days after activation)
	Enrollment	Baseline	Start Trial Phase	End Trial Phase (up to 10 days after trial starts)	Permanent Implant (up to 60 days after end of trial)	Device Activation (0-14 days after implant)	1-month visit (±15 days after activation)	3 months visit (±21 days after activation)	6 months visit (±31 days after activation)	
Informed Consent	X									X b)
Pain Intensity Evaluation (VAS)	X			X			X	X	X	X
Medication Use	X	X	X	X	X	X	X	X	X	X
Medical/Surgical History	X	X								
Eligibility Criteria Evaluation	X									
Pain Disability Questionnaire		X							X	X
AP/Lateral x-ray imaging			X	[X]	X	[X]	[X]	X	[X]	[X]
Paresthesia Questionnaire								X	X	X
Patient Global Impression of Change								X	X	X
Subject Satisfaction								X	X	X
Adverse Event Monitoring		X	X	X	X	X	X	X	X	X
Device Programming			X			X	[X]	[X]	[X]	[X]
Device Programming Log				[X]			[X]	[X]	[X]	[X]
Study Completion				X a)				[X] c	[X] c	X c

[X] Optional activity.

a) For subjects that do not have a successful Trial Phase.

b) Some subjects may need to be reconsented to complete these visits.

c) Some subjects were originally consented to complete the study at the 3 or 6 month visit and may not consent for additional visit.

## C. RISK ANALYSIS

### C.1. DESCRIPTION AND ANALYSIS OF ALL INCREASED RISKS TO SUBJECTS

DTM SCS programming approach will be used with a commercially available, FDA approved, Intellis™ SCS system, with parameters within the specifications for the indicated use. Anticipated potential adverse events resulting from the study are expected to be in line with adverse events already documented for SCS using a conventional programming approach.

There are known risks associated with the use of any SCS system. Known risks are associated with the implant procedure, the stimulation, the implanted device (not associated with stimulation) and external devices such as the charger and remote control. These are typical of commercial SCS systems. Subjects will be informed of these anticipated risks in the study consent process.

#### ***Risks of Surgery:***

Implanting a neurostimulation system has risks similar to spinal procedures, including spinal fluid leak (spinal fluid collection under the skin), headaches, swelling, bruising, bleeding, infection, or paralysis.

Subjects on anticoagulation therapy may be at higher risk for problems after surgery such as hematomas that could result in paralysis.

#### ***Spinal Cord Stimulation Risks:***

The implantation of a spinal cord stimulation system involves risks that are similar to other spinal procedures. In addition to those normally associated with surgery, implantation or use of a neurostimulation system includes, but is not limited to, the following risks:

- Allergic or immune system response to the implanted materials
- Infection
- Lead or neurostimulator erosion through the skin or migration
- Leakage of cerebrospinal fluid
- Loss of pain relief may return patients to their underlying pain condition
- Persistent pain at the neurostimulator site
- Placement of the epidural lead is a surgical procedure that may expose patients to risks of epidural hemorrhage (bleeding), hematoma, or paralysis
- Radicular chest wall stimulation
- Seroma (fluid collection in pocket where stimulator is placed) or hematoma at the neurostimulator site

- Change in stimulation, possibly related to cellular changes around the electrode(s), shifts in electrode position, loose electrical connections, lead fractures, which has been described by some patients as uncomfortable stimulation (jolting or shocking sensation)
- Over time, there could be changes in the level of symptom control. In most cases, the physician can correct these changes without surgery.
- Formation of excessive tissue around the lead in the epidural space can result in delayed spinal cord compression and paralysis, requiring surgical intervention. Time to onset can range from weeks to many years after implant.
- The safety of this therapy is unknown for pregnancy, unborn fetus, or delivery
- Stimulation-dependent gastrointestinal symptoms such as diarrhea, incontinence or constipation
- Stimulation-dependent bladder symptoms such as urinary retention, incontinence or frequency
- Unexpected changes in stimulation - Electromagnetic interference, changes in posture, and other activities can cause a perceived increase in stimulation

***System Revision Risk:***

The Intellis Neurostimulator may require replacement in 9 years or earlier, regardless of the number of times the neurostimulator is recharged. It is possible that the system will need to be revised (explanted, replaced, or repositioned) earlier than 9 years. Possible reasons for revision/explant may include infection, malfunction, and migration of the system components. The risks associated with system revision are equivalent to the commercially available systems.

***Pregnancy Risks***

Pregnant women are not able to take part in this study. Female subjects must agree to not become pregnant during the study by using a medically acceptable method of birth control. If a subject becomes pregnant during this study, there may be risks to the unborn child that are not yet known. Subjects will be advised and encouraged to notify the study doctor immediately if they think they are or have become pregnant. Subjects that become pregnant during the study will be instructed to turn the neurostimulator “OFF” and will be exited from the study.

***Radiographic Imaging***

As part of the study, subjects maybe required to have fluoroscopic or X-ray images taken of their thoracic spine. in addition to the imaging conducted to implant the leads. This may be beyond what is standard of care. The risk associated with these additional images has been considered and determined to be minimal since the total radiation dose will be approximately the same as one CT scan of the abdomen.

***Study Risk Control Measures***

The following will be done to mitigate risks associated with the implanted system:

- Investigators who are experienced with spinal cord stimulation implantation techniques will be utilized
- Instructions will be given to the study participants to ensure they can properly use the patient programmer and recharger system
- Subjects can turn off stimulation at any time during the study with the patient programmer or recharger
- Periodic monitoring of the study participants
- Written materials that contain precautions, warnings, and contraindications, as well as instructions on the use of the devices will be available and/or provided to the clinicians and subjects

Since the efficacy measure in this study is intensity of pain in the upper limbs, pain in these areas does not need to be reported as an adverse event unless it meets the definition of a serious adverse event. However, Investigators may, at their discretion, report any other pain-related adverse events during the study.

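### Reporting of pain outside the upper limb is optional in two places but mandatory for study-related events elsewhere, so non-serious device- or procedure-related pain can be under-counted

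*Combined protocol and SAP*

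**What the plan says.** Two sections deal with pain as an adverse event. In Section C.1 (Study Risk Control Measures), upper limb pain is exempt because it is the effectiveness measure: "pain in these areas does not need to be reported as an adverse event unless it meets the definition of a serious adverse event". The next sentence turns to all remaining pain: "However, Investigators may, at their discretion, report any other pain-related adverse events during the study". Section B.8.3.1 has the same exemption followed by a similar permission: "Investigators may, however, report any other study pain-related adverse events during the study". The B.8.3.1 sentence does not contain the words on discretion; those stand only in C.1.

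Other provisions are mandatory and make no exception for pain outside the upper limb. Section B.8.3.1: "For all study-related adverse events, the Investigator will provide an assessment of the adverse event, its seriousness, treatment/intervention provided". Section B.8.3.2: "All study-related adverse events will document seriousness, severity, treatment/intervention provided, relationship to the device/procedure/therapy, and resolution". Section E.3 makes the Investigator responsible for recording study-related events and assessing their relationship and seriousness, and requires serious ones to reach the sponsor within 48 hours. Section B.8.3 builds the safety evaluation on these records: "Safety will be assessed by characterizing study-related adverse events at all study visits with descriptive statistics". Section B.7.4 makes adverse event frequency a secondary endpoint.

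The list of stimulation risks in Section C.1 includes "Persistent pain at the neurostimulator site", and the surgical risks there include headaches.

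**The concern.** The reason given for exempting upper limb pain is that it is already measured as the effectiveness outcome. That reason does not extend to pain at the neurostimulator or lead site, neck pain or headache. If such pain results from the device, procedure or therapy, it is a harm of the kind the safety objective is meant to describe.

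The permissive sentences cover this pain without limiting themselves to events judged unrelated. The same non-serious event can therefore be optional under one part of the plan and required under another. Investigators at several centres may resolve the conflict differently. A low frequency of pain events could then reflect good tolerability or non-reporting, and a reader of the results could not easily tell which.

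**Working it through.** The plan states no adverse event rate and no reporting rate, so there is no figure to reproduce. The check is a comparison of the provisions, followed by an illustration on assumed rates.

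**Step 1: the provisions side by side, for a non-serious, study-related pain at the neurostimulator site.**

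| Provision | Effect on this event |
|---|---|
| C.1, Study Risk Control Measures | Reporting optional, at the Investigator's discretion |
| B.8.3.1, sentence after the upper limb exemption | Reporting optional (*may*) |
| B.8.3.1, assessment duty | Required: applies to all study-related events |
| B.8.3.2, documentation duty | Required: applies to all study-related events |
| E.3, recording duty | Required: Investigator responsible |
| E.3, 48-hour rule | Does not apply: serious events only |

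The capture rule in B.8.3.2, "Only adverse events that are evaluated by the Investigator to be study-related will be captured on the CRF", is a filter. It keeps unrelated events off the CRF but does not itself say that every related event goes on. The duty to cover all of them comes from the sentence that follows it, from B.8.3.1 and from E.3. No provision says which rule prevails.

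**Step 2: direction.** Optional reporting can remove events from the count and cannot add any. If there is an effect on the recorded frequency of these events, it is downward.

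**Step 3: illustration.** Inputs:
- n = 45 implanted subjects (Section B.5.4.1).
- True rate p of non-serious study-related pain outside the upper limb: assumed 10%, with a range of 5% to 20%.
- Probability r that such an event is reported: assumed 25% to 100%.
- One event per subject (assumed).

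Formulas: expected true count = n × p; expected reported count = n × p × r; apparent rate = p × r; chance that no event is reported = (1 − p × r)^n.

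At p = 10% the expected true count is 45 × 0.10 = 4.5.

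| r | Expected reported | Apparent rate | Chance none is reported |
|---|---|---|---|
| 100% | 4.5 | 10.0% | 0.90^45 = 0.9% |
| 75% | 3.4 | 7.5% | 0.925^45 = 3.0% |
| 50% | 2.25 | 5.0% | 0.95^45 = 9.9% |
| 25% | 1.1 | 2.5% | 0.975^45 = 32.0% |

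Over p from 5% to 20% and r from 25% to 75%, the apparent rate runs from 0.05 × 0.25 = 1.25% to 0.20 × 0.75 = 15%.

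Events are captured from enrollment, and about 55 subjects are expected to be trialed. With n = 55, the 10% and 50% case gives 5.5 true and 2.75 reported events. The apparent rate is still 5%.

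**The case against.** The strongest reply is that the mandatory duties already settle the matter. B.8.3.1, B.8.3.2 and E.3 cover study-related events without exempting pain, the visit descriptions call for adverse event assessment, and the section devoted to reporting contains no discretion. On that view the permissive sentence only says that the upper limb exemption does not bar other pain reports, or it concerns pain not judged study-related. This reading is possible for B.8.3.1, which says only *may*. It does not fit C.1, because a required report is not discretionary, and neither sentence is limited to unrelated pain. What stands is that the plan is contradictory rather than clearly permissive. A reader might infer that a site reporting no such pain would be fully compliant. The documents do not support that, since the site could still fail the duties in B.8.3.1, B.8.3.2 and E.3.

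A second reply is that missed events could be recovered. Unscheduled visits are recorded on a CRF (B.6.9), other pain is scored at 3, 6 and 12 months if available (B.7.5), monitors check CRFs against source records (E.1.2), and data are reviewed for study-related events (E.2). So it would be too strong to say that the loss is beyond repair. These backstops are partial: a pain score, for example, carries no judgement of relatedness or resolution.

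Third, the analysis is descriptive and no comparison across sites is planned (B.9.2), so variation between Investigators defeats no planned analysis. That is true, but the pooled frequency would still be affected.

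**Conclusion.** The conflict is real and should be resolved. Non-serious study-related pain outside the upper limb can be under-counted in a secondary safety endpoint, to a degree that may differ by Investigator. The primary endpoint is untouched, and serious study-related events remain mandatory.

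A reader might go further and conclude that the endpoint is in fact under-counted by an amount that varies by site. The documents do not show this. Loss occurs only where an Investigator treats the permissive sentence as overriding the duties elsewhere, and nothing in the plan indicates how often that would happen. The size is therefore not derivable. The drop from 10% to 5% rests wholly on an assumed true rate, an assumed reporting probability and one event per subject; it shows how the mechanism works and is not an estimate.

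**What to change.** In Section B.8.3.1 and in Section C.1 (Study Risk Control Measures), replace the permissive sentence with: *Any pain outside the upper limb that the Investigator judges related to the device, procedure or therapy is recorded as an adverse event on the CRF.* This brings both places into line with B.8.3.2 and E.3 and leaves the upper limb exemption as it is. Tabulating these events by location (neurostimulator site, lead site, neck, headache, other) would help readers but is optional.

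The cost is one sentence in two places, a few more adverse event forms, and a reported frequency that may look less favourable. The change does not remove differences between Investigators in judging relatedness, which B.8.3.2 already leaves to them. It removes only the separate choice not to report an event already judged related.
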